## 1. Participant Flow

[figure not shown]
The number of participants who started and completed this study is shown in Figures 1, 2, 3, and 4.

[figure not shown]
**Figure 1.** A CONSORT flow diagram for young males.

**Figure 2.** A CONSORT flow diagram for young females.

**Figure 3.** A CONSORT flow diagram for older males.

**Figure 4.** A CONSORT flow diagram for older females.

based on self-report of onset of menses and previous menstrual cycle length.

Arm 3:

Trial for older male participants (aged 40 – 65 years): Consuming HC with RE.

Arm 3 Description:

The intervention procedure is the same as Arm 1.

Arm 4:

Trial for older female participants (aged 40 – 65 years): Consuming HC with RE.

Arm 4 Description:

The intervention procedure is the same as Arm 2.

## **Period**

Period title:

Overall study

Participants were recruited from a university student population (young participants) and from the local area (older participants). Recruitment began in January 2019 and data collection was completed in September 2021.

### **3. Outcome Measure Information**

Table 1 shows data for each primary and secondary outcome measure by arm.

**Table 1.** Data for outcome measures.

#### **Outcome Measure Title and description**

Concentrations of serum procollagen type I N-terminal propeptide (PINP) (ng/mL)

Concentration of plasma  $\beta$ -isomerized C-terminal telopeptide of type I collagen ( $\beta$ -CTX) ( $\mu$ g/L)

Concentration of 18 amino acids that constitute collagen ( $\mu$ mol/L):

Glycine, proline, hydroxyproline, glutamic acid, alanine, arginine, aspartic acid, lysine, serine, leucine, valine, phenylalanine, threonine, isoleucine, histidine, tyrosine, methionine, and glutamine.

Concentration of 17 $\beta$ -estradiol (pg/mL)

#### **Outcome Measure Time Frame**

Outcome measures were analyzed from September 2019 to August 2022

#### **Arm 1 Information**

Arm 1 title:

Young male trials

Arm 1 description:

Thirteen male participants volunteered for this study but three were excluded prior to participation due to not meeting the inclusion criteria ( $n = 1$ ) and declining to proceed with participation ( $n = 2$ ). Therefore a total of 10 male participants completed the study, which included three separate trials.

## **Arm 2 Information**

Arm 2 title:

Young female trials

Arm 2 description:

One female participant completed this study, which included four separate trials.

## **Arm 3 Information**

Arm 3 title:

Older male trials

Arm 3 description:

Ten male participants volunteered for this study but two were excluded prior to participation due declining to proceed with participation. Therefore a total of eight male participants completed the study, which included three separate trials.

## **Arm 4 Information**

Arm 4 title:

Older female trials

Arm 4 description:

Two female participants completed this study, which included four separate trials.

### **Analysis Population Information**

In Arm 1, data from 10 male participants were analyzed and in Arm 2, data from one female participant were analyzed. In Arm 3, data from 8 male participants were analyzed and in Arm 4, data from two female participants were analyzed.

### **Outcome Measure Data Table**

Outcome measure data are shown in Table 2.

**Table 2.** Outcome Measure Data.

Variable	Measure type	Measure of Dispersion
Arm 1		
Serum PINP (ng/mL)	Mean	Standard deviation
Plasma $\beta$ -CTX ( $\mu$ g/L)	Mean	Standard deviation
18 Serum amino acids ( $\mu$ mol/L)	Mean	Standard deviation
Arm 2		
Serum PINP	n/a	n/a

---

(ng/mL)		
Plasma $\beta$ -CTX	n/a	n/a
( $\mu$ g/L)		
18 Serum amino acids	n/a	n/a
( $\mu$ mol/L)		
Serum 17 $\beta$ -estradiol	n/a	n/a
(pg/mL)		
Arm 3		
Serum PINP	Mean	Standard deviation
(ng/mL)		
Plasma $\beta$ -CTX	Mean	Standard deviation
( $\mu$ g/L)		
18 Serum amino acids	Mean	Standard deviation
( $\mu$ mol/L)		
Arm 4		
Serum PINP	n/a	n/a
(ng/mL)		
Plasma $\beta$ -CTX	n/a	n/a
( $\mu$ g/L)		
Serum 18 amino acids	n/a	n/a
( $\mu$ mol/L)		
Serum 17 $\beta$ -estradiol	n/a	n/a
(pg/mL)		

---

## Statistical Analyses

Due to the sample size ( $n=1$ ) in Arm 2, only data from Arm 1 were analyzed.

Two-way within-subject ANOVA models (dose  $\times$  time) were performed to detect changes in serum PINP, amino acid and plasma  $\beta$ -CTX concentration. One-way repeated measures ANOVA models were performed to detect differences in area-under-the-curve between trials for PINP and each of the 18 amino acids. If an interaction effect or a main effect of HC dose existed, Bonferroni post-hoc pairwise comparisons were performed. The level of statistical significance was set at  $P < 0.05$ .

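### With three conditions per man, the AUC analysis corrects its pairwise comparisons twice (omnibus F gate, then Bonferroni) and so loses power to show which doses differ.

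*Combined protocol and SAP*

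**What the plan says.** The section Statistical Analyses describes the AUC comparison as follows: "One-way repeated measures ANOVA models were performed to detect differences in area-under-the-curve between trials". This covers 19 outcomes, namely PINP and the 18 amino acids, with a threshold of 0.05 for significance. The follow-up rule is "If an interaction effect or a main effect of HC dose existed, Bonferroni post-hoc pairwise comparisons were performed". I read this rule as covering the AUC models as well as the two-way models; for a one-way model only the dose effect can trigger it.

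The same section says that "only data from Arm 1 were analyzed". Analysis Population Information gives the number: "In Arm 1, data from 10 male participants were analyzed". (It also lists Arm 3, with 8 men, as analysed. I follow Statistical Analyses here.) Arm 1 Information says that each man completed three trials.

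The documents do not state the error term of the pairwise tests (separate paired t or pooled ANOVA error), any correction for non-sphericity, a family error rate, a power figure, an effect size or an SD.

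**The concern.** The omnibus gate and the Bonferroni divisor guard against the same error. For three conditions there are three pairwise null hypotheses, and any two of them together imply that all three means are equal. The only intersection that a closed test must reject before it looks at a pair is therefore the global null, which the F test covers at 0.05. If one dose truly differs from two equal ones, a single true null pair remains, and testing it at 0.05 keeps the family error at 5%. Dividing by three as well buys no further control that the stated level calls for, provided that the gate itself is valid.

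What is at stake is interpretation in a sample of 10. A pair that is non-significant after a significant dose effect may reflect the doubled correction rather than similar responses at the two doses.

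**Working it through.** **Inputs from the documents.** n = 10 men and 3 trials each; alpha 0.05; 19 AUC models (PINP plus 18 amino acids). There is no stated power or family error to reproduce.

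**Degrees of freedom and thresholds.** Dose 3 - 1 = 2; error (10 - 1)(3 - 1) = 18; separate paired t 10 - 1 = 9. The two-sided critical t with 9 df is 2.26 at 0.05 and 2.93 at 0.05/3 = 0.0167. Since 2.93/2.26 = 1.30, Bonferroni asks for an observed difference about 30% larger relative to its standard error. With a within-person SD of 1, the standard error of a difference is about √(2/10) = 0.447, so the bar moves from about 2.26 × 0.447 = 1.01 SD to 2.93 × 0.447 = 1.31 SD.

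**Partial null, by reasoning.** If one dose differs enough for the gate to open almost always, only one true null pair is left. Its error is then close to 0.0167 under the plan's rule, against 0.05 under the closed test.

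**Simulation.** Assumptions: normal data, n = 10, equal variances and correlations, differences in units of the within-person residual SD. The omnibus F at 0.05 rejected in 5.06% of null runs, which checks the code.

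| Setting | Pair test | F gate + Bonferroni | F gate + pairs at 0.05 (closed) |
|---|---|---|---|
| Family error, no dose effect | separate t | 3.1% | 5.0% |
| Family error, no dose effect | pooled | 4.2% | about 5% |
| Family error, one dose differs by 1 SD or more | separate t | 1.5-1.7% | 4.5-5.0% |
| Family error, one dose differs by 1 SD or more | pooled | 1.6-1.7% | about 5% |
| Power per true pair, plateau 0/1.2/1.2 | separate t | 43-44% | 61% |
| Power per true pair, plateau 0/1.2/1.2 | pooled | 53% | 65% |
| Power, lowest against highest, linear 0/0.7/1.4 | separate t | 57% | 71% |
| Power, lowest against highest, linear 0/0.7/1.4 | pooled | 68-69% | 72-73% |

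The gain in power thus runs from about 4 points (pooled, linear) to about 17 points (separate t, plateau).

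**Holm in place of Bonferroni.** At the 1.2 SD plateau with separate t tests, power per true pair is about 47% with the F gate kept and 48% without it.

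**Sphericity.** The closed test is only as good as its gate. In one non-spherical example its family error was 6.2% with an uncorrected F and 4.9% with a Greenhouse-Geisser gate. With sphericity true, the corrected gate followed by separate paired t tests gives 4.1% under the global null. At the 1.2 SD plateau it gives 59% power per true pair, against 42% for Bonferroni behind the same gate. The corrected gate opens less often in that setting, 68% against 72%.

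**The case against.** **The plan is valid as it stands.** An omnibus F followed by Bonferroni is standard and conservative, and the section promises no family error to be spent exactly. This stands: the point is lost efficiency, not an inflated error.

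**Bonferroni gives some insurance.** With condition SDs of 0.5, 0.5 and 2, an uncorrected closed test with separate t tests has 6.4% family error against 2.5% under the plan's rule. This stands against an uncorrected gate, and it is why the fix includes Greenhouse-Geisser.

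**The size depends on an unstated choice.** This also stands. A reader might take 1.5-3% as the plan's true error, but that holds only for separate t tests; with the pooled term the global-null figure is 4.2%.

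**A reader might infer that the plan can miss a dose effect on PINP because of Bonferroni.** The documents do not support this. The omnibus F is the test of a dose effect, and it runs at the full 5%.

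**A reader might also want a linear dose contrast as the main test.** Its advantage depends on the response shape. For linear 0/0.7/1.4 it has 79-84% power against 73% for the omnibus F. For a single step of 1.2 SD it has 67-72% against 72%, and it has only 5% if the middle dose alone differs. Nothing in the documents points to one shape. The Arm/Group Information also lists the doses as 0, 15 and 15 g while matching calories to 30 g, and these statements must be reconciled before any ordered contrast can be defined. The closed test needs only three conditions, not an order.

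**The larger error problem runs the other way.** Nineteen AUC models at 0.05 each give 1 - 0.95^19 = 62% chance of at least one false positive if they were independent. That is a separate matter, and it limits what any per-outcome rule can claim.

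**Conclusion.** The second correction is redundant with three conditions. It holds the family error of pairwise claims to about 1.5-4.2% per outcome and costs roughly 4 to 17 points of pairwise power in the settings examined. Detection of a dose effect is not affected by it.

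The gain from the recommended fix depends on what was actually run. If the original used separate t tests behind an uncorrected gate, the 1.2 SD plateau moves from 43-44% to 59%. If it used the pooled term, the same pair moves only from 53% to 59%, and the lowest-against-highest pair under 0/0.7/1.4 stays at about 68%; the fix then mainly adds robustness to non-sphericity.

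The error results rest on normal data and the closed-testing argument. The powers rest on effect sizes that I assumed, since the documents supply none. This is an inexpensive improvement to the analysis, not a flaw that invalidates it.

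**What to change.** For each AUC, run the omnibus test with a Greenhouse-Geisser correction and, if it is significant at 0.05, test the three pairs by separate paired t tests at 0.05 each. The simpler alternative is Holm in place of Bonferroni: it rejects at least everything that Bonferroni rejects, but recovers much less. In either case, state the error term that the original pairwise tests used.

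Data collection ended in September 2021 and outcomes were analysed up to August 2022, so the re-run comes after the results. Report it beside the original analysis, label it post hoc, and do not let it replace the original.

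The cost is a few sentences and a re-run on existing data. There are three downsides. Neither procedure yields simple simultaneous confidence intervals, though the plan promises none. The corrected gate gives up a little omnibus power when sphericity holds (72% to 68% at the 1.2 SD plateau). Control is within each outcome only, not across the 19 AUC models, and the report should say so.

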#### **4. Adverse Event Information**

During data collection period, any adverse event such as all-cause mortality or serious adverse event did not occur.

#### **5 Certain Agreements**

Are all PIs Employees of Sponsor?

No: The principal investigator is a PhD student, not an employee of the sponsor

Results Disclosure Restriction on PI(s)?

No

